7.5. Supplies and Accountability

Sites will be instructed to store the study medication at room/ordinary temperature (15°C to 25°C / 59°F to 77°F) in a secure area, free from environmental extremes, and with

restricted access. The capsules must be dispensed to subjects in the original study medication container provided by the sponsor.

Investigational product must be stored in a secure area under the appropriate physical conditions for the product. Access to and administration of the investigational product will be limited to the investigator and authorized site staff. Investigational product must be dispensed or administered only to subjects enrolled in the study and in accordance with the protocol.

The investigator, or appropriately assigned designee, will inventory and acknowledge receipt of all shipments of the study medication. The investigator agrees to keep accurate records of the quantities of study medication dispensed, used, and returned by each subject. Subjects will be instructed to return all unused, partially used, or empty study medication containers at the specified visits. The study monitor will periodically check the supplies of study medication held at the site to verify accountability of all study medication used and to verify that a final report of drug accountability to the unit dose level is prepared and maintained in the investigator study file. When instructed by the monitor, the investigator agrees to return all original containers of study medication, whether empty, or containing used or unused study medication to the sponsor or their designee.

7.6. Treatment Compliance

Dosing compliance will be assessed at each clinic visit through subject interview and comparison of the amount of study medication the subject was scheduled to take over the number of days during the study with the amount returned.

The investigator may choose to interrupt or discontinue the study medication in case of an AE. Any interruption in dosing for this, or other reasons, must be documented.

The investigator should discontinue the study medication if continued administration of the study medication is believed to be contrary to the best interest of the subject. The reasons for discontinuation must be documented.

If the reason for the interruption or discontinuation of the study medication is an AE, an abnormal assessment (e.g., ECG finding), or a laboratory test abnormality, this information will be recorded as an AE.

If the subject is not compliant with the study medication administration, the investigator may need to evaluate whether the noncompliance should warrant subject withdrawal from the study.

7.7. Prohibited Medications and Non-Drug Therapies

Use of investigational/experimental therapy is not allowed at any time during the study.

Routine use of the following medications during this trial is prohibited:

- Glyset (miglitol)
- Zavesca (miglustat)
- Fabrazyme (agalsidase beta)

- Replagal (agalsidase alfa)

If the subject receives investigational therapy, or if routine use of prohibited medications is initiated, the subject must be prematurely discontinued from the trial and final assessments performed at the last treatment visit.

Drugs that affect lysosomal pH (e.g., chloroquine) and drugs that result in accumulation of phospholipids in lysosomes (e.g., gentamicin, amiodarone) should be avoided due to the theoretical potential for interactions with migalastat. If alternative therapies exist these should be used.

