6.4. Withdrawal Criteria

Subjects may discontinue migalastat HCl and withdraw from the study for any reason including, but not limited to, the following:

- At their own request or at the request of their parent or guardian (if the subject is a minor) or legally authorized representative*.
- If, in the investigator's opinion, continuation in the study would be detrimental to the subject's well-being.
- Occurrence of an intolerable adverse event (AE) as determined by the investigator and/or the subject.
- Subject initiates or plans to initiate regular ERT for Fabry disease.
- Suspected hepatotoxicity, as defined by increase of ALT or AST $\geq 3X$ upper limit of normal (ULN) and total bilirubin $> 2X$ ULN when no other reason can be found to explain the increase in liver enzymes.
- Persistent noncompliance with study requirements, such as failure to return to the study site for scheduled visits.
- Pregnancy and/or breast feeding.
- Documented eGFR_{MDRD} value meeting the criteria defined below:
 - An eGFR value (calculated centrally) that is < 30 mL/min/1.73m²

In all cases, the reason for withdrawal and the date of withdrawal must be recorded in the electronic case report form (eCRF) and in the subject's medical records.

* “Legally authorized representative” means an individual or judicial or other body authorized under applicable law to consent on behalf of a prospective subject to the subject's participation in the procedure(s) involved in the research.

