- ⁷ Study Treatment Supply for Study AT1001-042 is intended to occur on Baseline (Visit 1) or in subsequent days within the allowable window for this visit.
- ⁸ Subjects will receive a telephone contact, or contact using another acceptable method, approximately midway between visits to assess Adverse Events and dosing compliance. It is better to have the phone contact performed earlier or later than scheduled, rather than not at all.

Baseline

During transition from the previous study into the current study, the intent is for treatment with migalastat HCl to continue without a break.

Assessments collected as a part of the last treatment visit in the previous study, that are also required for the Baseline Visit in the current study, will serve as the assessment for the Baseline Visit. The visit window for the last treatment visit in the previous study will apply to those Baseline Visit assessments. However, to provide flexibility to investigators and subjects, any Baseline Visit assessment that is required for the current study and not a required assessment for the last treatment visit in the previous study, may be performed up to 30 days after entry into the current study.

Unscheduled visits

Unscheduled visits can be performed at any time point at the investigator's discretion for medical reasons, such as evaluation of AEs and/or repeat laboratory tests.

Early Withdrawal

Subjects who meet any of the withdrawal criteria in Section 6.4 and withdraw from the study will be asked to return for a visit approximately 30 days after last treatment and have end of study assessments performed as shown in Table 1. An echocardiogram (ECHO) will be performed for subjects who have not had an ECHO within the previous 6 months.

End of Study

An End of Study visit will occur within approximately 30 days of the subject's last treatment dose.

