10. DISPOSITION AND WITHDRAWALS

All subjects who provide informed consent will be accounted for in this study. Number of subjects, subject discontinuation, and primary reason for discontinuation will be presented for the ITT and Addendum 1.1.2 population.

The list of primary reasons for discontinuation (as per CRF) can be referred to as below:

- Screen Failure
- Adverse Event
- Subject Met Protocol Defined Stopping Criteria
- Physician Decision
- Lost to Follow-up
- Non-Compliance with Study Requirements
- Pregnancy and/or Breast feeding
- Protocol Violation
- Withdrawal by Subject
- Study Terminated by Sponsor
- Death
- Other

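### For a subject who starts ERT, the protocol gives two different times for the final assessments, and the visible SAP text does not settle whether those values enter the AT1001 efficacy summaries or plan a count of on-study ERT starts.

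*Protocol*

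**What the plan says.** **Timing of final assessments.** Protocol 7.7 lists both agalsidase products among the medications whose routine use is prohibited. If such use begins, "the subject must be prematurely discontinued from the trial and final assessments performed at the last treatment visit". Starting ERT is also an entry in Protocol 6.4: "Subject initiates or plans to initiate regular ERT for Fabry disease". For anyone who withdraws on a 6.4 ground, the Early Withdrawal paragraph of Section 8 says that they "will be asked to return for a visit approximately 30 days after last treatment". Table 1 has one final column, End of Study, at about 30 days after the last dose. It has no last-treatment or early-termination column.

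**Whether the subject leaves.** Protocol 6.4 opens with "Subjects may discontinue migalastat HCl and withdraw from the study for any reason including, but not limited to, the following". Section 7.7 uses *must*.

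**SAP, efficacy values.** Section 17.1 summarizes efficacy by nominal visit and leaves out unscheduled and early-termination visits. Section 17.1.1 fits the MDRD eGFR slope over each subject's available visits from baseline to End of Study. Appendix 1 shows End of Study as a displayed visit and labels every summary AT1001.

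**SAP, ERT reporting.** Section 10 introduces its reasons with "The list of primary reasons for discontinuation (as per CRF) can be referred to as below"; none of the 12 is starting ERT. Section 14 plans a medication table by ATC level 3 and preferred term, a full medication listing and a listing of ERT history. Section 11 has a general category for concomitant-medication deviations.

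**The concern.** A subject who leaves migalastat for ERT has a last set of eGFR, lyso-Gb3, WBC α-Gal A and other efficacy values. Those values describe migalastat only if they were taken before ERT began and while migalastat was still being taken. The protocol gives sites two instructions on when to take them, and the visible SAP text does not use ERT status or last-dose date to sort them. Two similar subjects at two sites could contribute final values from different treatment states under the same AT1001 label.

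A reader of a long-term extension study will also want to know how many subjects moved to ERT and when. No planned output in the visible text gives that figure. SAP 7.2 names AT1001-012 as a feeder study, and Protocol 3.2 describes its population as ERT-experienced. An agalsidase row in the medication table or an entry in the ERT history listing may therefore reflect use before entry. The medication table has no stated split between prior and on-study use.

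The effect is on the secondary efficacy/pharmacodynamic objective. The study is descriptive, so no test or error rate is involved.

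**Working it through.** The plan states no figure on this point, so there is none to reproduce. The check sets the passages side by side and then gives a scale.

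**1. Protocol rules for a subject who starts routine ERT**

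| Source | Leaves the study? | Final assessments |
|---|---|---|
| Protocol 6.4 | may | not stated |
| Protocol 7.7 | must | last treatment visit |
| Protocol 8, Early Withdrawal | applies to those who meet a 6.4 criterion and withdraw | about 30 days after last dose |
| Protocol Table 1 | not stated | one final column, about 30 days after last dose |

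On timing, the second row cannot be met together with the third and fourth. The separate End of Study paragraph in Section 8 allows a visit within about 30 days, but the Early Withdrawal paragraph is the one addressed to subjects who withdraw.

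**2. What fits into the gap**

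The Protocol Summary gives the ERT interval as two weeks. 30 days / 14 days = 2.14, so two full intervals fit. If the first infusion falls on the day of the last migalastat dose, infusions on days 0, 14 and 28 precede the visit (three). If it falls one interval later, two do. If ERT starts after day 30, none do, and the values are then off migalastat but not on ERT. Section 7.7 is itself triggered by the start of routine use, so a last treatment visit could also follow a first infusion. Neither timing rule alone fixes the treatment state.

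**3. What the SAP does with the visit**

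- If it is early termination, SAP 17.1 excludes it from efficacy summaries.
- If it is End of Study, it is a displayed visit and lies inside the slope interval of SAP 17.1.1.
- The schedule (Protocol Table 1, repeated as SAP Table 1) and the visit labels in SAP Appendix 1 contain End of Study but no early-termination visit.

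The text does not say which applies.

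**4. Scale for one subject's eGFR slope (illustration)**

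Assumptions: visits every 6 months, End of Study 30 days after the last of them, and a shift d of 2 to 5 mL/min/1.73m² in either direction in the End of Study value. The size of d is assumed; the documents give none.

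Change in slope = d × (t_EOS − mean t) / Sxx, where Sxx = Σ(t − mean t)².

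For one year, t = 0, 0.5, 1 and 1 + 30/365.25 = 1.082. Then mean t = 0.646, Sxx = 0.754 and the multiplier is (1.082 − 0.646)/0.754 = 0.579.

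| Follow-up | Values in slope | Change for d = 2 | Change for d = 5 |
|---|---|---|---|
| 1 year | 4 | 1.16 per year | 2.89 per year |
| 2 years | 6 | 0.52 per year | 1.30 per year |
| 4 years | 10 | 0.20 per year | 0.50 per year |

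**5. Scale for a group mean**

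Protocol 6.1 expects up to 100 subjects. One affected subject at the largest value above moves a mean over 100 slopes by 2.89/100 = 0.03 per year. SAP 8.5 splits the slopes into six sex-by-proteinuria subgroups. If these were equal in size (100/6 = 16.7, an assumption), the same subject moves a subgroup mean by 2.89/16.7 = 0.17 per year.

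**The case against.** Several stronger readings are tempting, and the documents do not support them.

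- **Section 6.4's *may* flatly contradicts 7.7's *must*.** A reader might infer this, but 6.4 is a general list of grounds. It also contains eGFR below 30, which Protocol 8.2.2 makes mandatory, and it covers merely planning ERT. A site that follows 7.7 satisfies both. Aligning the wording helps, but the two can be read as compatible.
- **The study cannot report how often ERT was started.** It can. Concomitant medications are recorded at the scheduled clinic visits and End of Study, the withdrawal reason goes into the eCRF, and medications and deviations are listed. What is missing is a planned ERT-specific count.
- **Post-ERT values do enter the AT1001 tables.** This is not established. SAP 17.1 excludes early-termination visits, which could remove some or all of them. Exclusion is not established either, because the visit type is undefined and the exclusion does not go by ERT status.
- **Every ERT starter is a treatment failure.** The documents do not say so. A subject may move to ERT after a mandatory stop or after local regulatory rejection, and some had ERT before. The documents also give no size for an ERT effect on WBC α-Gal A or lyso-Gb3.
- **Isolated infusions are permitted.** Section 7.7 prohibits routine use; it does not affirmatively allow occasional use.

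The strongest remaining objection concerns coverage. SAP 17.1.3 to 17.1.5 and part of 17.1.2 are not in the supplied text and may contain a relevant rule. That limits the SAP part to the sections that can be read and leaves the protocol timing conflict untouched.

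**Conclusion.** The timing conflict holds on the protocol's own wording: the last treatment visit in 7.7 against about 30 days after the last dose in Early Withdrawal and Table 1. The gap is long enough for two or three ERT infusions if ERT starts promptly.

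In the visible SAP text, whether an ERT starter's off-migalastat or on-ERT final values enter the by-visit and slope summaries cannot be determined, and no ERT-specific count of on-study starts is planned.

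The size for the study cannot be stated, because the number of starters and the effect of ERT on each endpoint are not given. In the illustration, one affected value moves an individual slope by 0.20 to 2.89 mL/min/1.73m² per year. The effect on a 100-subject mean is small, and it is larger in a subgroup. The consequence is for interpretation of the secondary efficacy/pharmacodynamic summaries. The correction is inexpensive and worth making.

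**What to change.** **Protocol.** Reconcile 7.7, 6.4, the Early Withdrawal paragraph and Table 1 so that one statement gives the timing of final assessments for a subject who starts ERT, and align *may* and *must* at the same time. Which clinical rule to adopt is for the sponsor and investigators; this review takes no view.

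**SAP.**
1. State whether that final visit counts as End of Study or as early termination, and apply the answer to both the by-visit summaries and the eGFR slopes.
2. Report the number, percentage and timing of subjects with any ERT use after the first dose in this study, from the concomitant-medication records.
3. Flag efficacy/PD values on or after first on-study ERT use, and show the by-visit and eGFR-slope summaries with and without them.

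Removing those values from the main tables, or adding a disposition reason for ERT, would be a matter of preference and is not needed.

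**Cost.** A clarifying protocol change, some SAP wording and a few extra outputs. No new data are required. The version without post-ERT data will hold slightly fewer values.

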7.8. Treatment after the End of the Study

The investigator is responsible for ensuring that consideration has been given to the post-study care of the subject's medical condition whether or not Amicus is providing specific post study treatment.

7.9. Treatment of Study Treatment Overdose

An overdose of migalastat HCl is defined as an ingestion of a dose greater than the prescribed dose of 150 mg migalastat HCl QOD. There are no known antidotes and Amicus does not recommend a specific treatment in the event of a suspected overdose. The investigators will use clinical judgment in treating the symptoms of a suspected overdose.

8. STUDY ASSESSMENTS AND PROCEDURES

The Time and Events Table displays each study assessment and procedure along with the scheduled time of occurrence ([Table 1](#)). All study assessments should be conducted by the investigator, and/or a suitably qualified designee. Information will be recorded in the source documents and, where appropriate, the eCRF.

All study visits should be scheduled from the Baseline Visit (Visit 1) as specified. Further information can be found in the SPM/ISFN.

Table 1: Time and Events Table

Study Month #	Baseline (Month 0) ¹	6 Months (±30 days)	12 Months (±30 days)	Repeat 6 & 12 Month visits in the subsequent years	End of Study (Approximately 30 days after last treatment)
Visit Number	V1	V2	V3	V4, V5, etc	
Assessments					
Review Informed Consent	X				
Review Inclusion/Exclusion Criteria	X	X	X		
Physical Examination	X	X	X		X
Concomitant Medications	X	X	X		X
Vital Signs (BP, HR, RR, Temp)	X	X	X		X
Weight	X	X	X		X
Height	X				X
12 Lead ECG	X	X	X		X
Echocardiography ²	X		X		X ³
Chemistry ^{4 5}	X	X	X		X
Hematology ⁵	X	X	X		X
Urinalysis ⁵	X	X	X		X
24-Hour Urine ⁵	X	X	X		X
eGFR calculation ⁵	X	X	X		X
WBC α-Gal A Activity ⁵	X	X	X		X
Pregnancy Test ⁶	X	X	X		X
Plasma Lyso-GB3	X	X	X		X
Adverse Events	X	X	X		X
SF-36 Survey	X	X	X		X
Study Treatment Supply/Resupply/Return ⁷	X	X	X		X
Intermediate Subject Contact ⁸	X	X	X		X

¹ Assessments collected for the last treatment visit in the previous study, which are also required at Baseline for the current study, will serve as Baseline Visit 1 assessments for this study. The visit window for the last treatment visit will apply for the completion of such assessments. Assessments required at Baseline (Visit 1) that are not performed as part of the last treatment visit in the previous study will have a visit window of +30 days.

² ECHOs will be read centrally.

- ³ ECHO is to be performed for subjects who withdraw from the study and did not have an ECHO performed within the previous 6 months.
- ⁴ Subjects must fast for approximately 8 or more hours before serum chemistry is performed.
- ⁵ In the event of an abnormal lab result, at the investigator's discretion, the test can be repeated in an unscheduled visit and sent to the central laboratory for analysis.
- ⁶ Urine pregnancy test to be performed at Baseline Visit 1 according to previous protocol; thereafter the urine pregnancy test will be performed locally using dipstick.
- ⁷ Study Treatment Supply for Study AT1001-042 is intended to occur on Baseline (Visit 1) or in subsequent days within the allowable window for this visit.
- ⁸ Subjects will receive a telephone contact, or contact using another acceptable method, approximately midway between visits to assess Adverse Events and dosing compliance. It is better to have the phone contact performed earlier or later than scheduled, rather than not at all.

Baseline

During transition from the previous study into the current study, the intent is for treatment with migalastat HCl to continue without a break.

Assessments collected as a part of the last treatment visit in the previous study, that are also required for the Baseline Visit in the current study, will serve as the assessment for the Baseline Visit. The visit window for the last treatment visit in the previous study will apply to those Baseline Visit assessments. However, to provide flexibility to investigators and subjects, any Baseline Visit assessment that is required for the current study and not a required assessment for the last treatment visit in the previous study, may be performed up to 30 days after entry into the current study.

Unscheduled visits

Unscheduled visits can be performed at any time point at the investigator's discretion for medical reasons, such as evaluation of AEs and/or repeat laboratory tests.

Early Withdrawal

Subjects who meet any of the withdrawal criteria in Section 6.4 and withdraw from the study will be asked to return for a visit approximately 30 days after last treatment and have end of study assessments performed as shown in Table 1. An echocardiogram (ECHO) will be performed for subjects who have not had an ECHO within the previous 6 months.

End of Study

An End of Study visit will occur within approximately 30 days of the subject's last treatment dose.

8.1. Critical Baseline Assessments

Fabry disease may result in end stage cardiovascular and renal disease and organ damage. Cardiovascular and other medical history and risk factors will be assessed at the Baseline Visit (Visit 1). The medical monitor or designee must be contacted to discuss the stability of a subject's medical condition(s) and the potential impact of the condition(s) on trial participation.

8.2. Safety

8.2.1. Safety Assessments

Safety assessments include the following:

- Adverse events (AEs), possible suicidality related adverse events (PSRAEs), and serious adverse events (SAEs)
- Withdrawal due to AEs
- Vital signs (blood pressure, body temperature, respiration rate, and heart rate) and weight
- Hematology, chemistry, and urinalysis parameters
- Echocardiography (ECHO)
- Electrocardiograms (ECGs)
- Stopping criteria

8.2.2. Stopping Criteria

Subjects must discontinue study medication and be withdrawn from the study if they meet any of the following stopping criteria:

- 30% increase in serum creatinine from Baseline (Visit 1) confirmed by repeat analysis in fully hydrated subject
- 25% decrease from Baseline in cardiac ejection fraction as determined by echocardiogram
- Cerebrovascular event with significant sequelae, including stroke
- An eGFR value of $< 30 \text{ mL/min/1.73m}^2$

8.2.3. Liver chemistry stopping and follow up criteria

Liver chemistry stopping and follow up criteria have been designed to assure subject safety and evaluate liver event etiology (in alignment with the FDA premarketing clinical liver safety guidance). Phase 3 criteria will be used for this study.

Phase III-IV liver chemistry stopping criteria 1-5 are defined below and in [Appendix 2](#).

1. ALT ≥ 3 xULN and bilirubin ≥ 2 xULN ($>35\%$ direct bilirubin) (or ALT ≥ 3 xULN and INR >1.5 , if INR measured)

NOTE: if serum bilirubin fractionation is not immediately available, withdraw study drug if ALT ≥ 3 xULN and bilirubin ≥ 2 xULN. Serum bilirubin fractionation should be performed if testing is available. If testing is unavailable, **record presence of detectable urinary bilirubin on dipstick**, indicating direct bilirubin elevations and suggesting liver injury.

2. ALT ≥ 8 xULN.
3. ALT ≥ 5 xULN but < 8 xULN persists for ≥ 2 weeks.

4. ALT ≥ 3 xULN if associated with symptoms (new or worsening) believed to be related to hepatitis (such as fatigue, nausea, vomiting, right upper quadrant pain or tenderness, or jaundice) or believed to be related to hypersensitivity (such as fever, rash or eosinophilia).
5. ALT ≥ 5 xULN but < 8 xULN and cannot be monitored weekly for ≥ 2 weeks.

When any of the liver chemistry stopping criteria 1-5 is met, do the following:

- **Immediately** withdraw investigational product.
- Report the event to Amicus **within 24 hours** of learning its occurrence.
- Complete the liver event CRF and SAE data collection tool if the event also meets the criteria for an SAE. All events of ALT ≥ 3 xULN **and** bilirubin ≥ 2 xULN ($> 35\%$ direct) (or ALT ≥ 3 xULN **and** INR > 1.5 , if INR measured); INR measurement is not required and the threshold value stated will not apply to patients receiving anticoagulants), termed ‘Hy’s Law’, **must be reported as an SAE (excluding studies of hepatic impairment or cirrhosis)**.

NOTE: if serum bilirubin fractionation is not immediately available, withdraw study drug if ALT ≥ 3 xULN **and** bilirubin ≥ 2 xULN. Serum bilirubin fractionation should be performed if testing is available. If testing is unavailable, **record presence of detectable urinary bilirubin on dipstick**, indicating direct bilirubin elevations and suggesting liver injury.

- Complete the liver imaging and/or liver biopsy CRFs if these tests are performed.
- Perform liver event follow up assessments, and monitor the subject until liver chemistries resolve, stabilize, or return to baseline values as described below.
- Withdraw the subject from the **study** (unless further safety follow up is required) after completion of the liver chemistry monitoring as described below.
- Do not re-challenge with investigational product.

In addition, for criterion 1:

- Make every reasonable attempt to have subjects return to the clinic within **24 hours** for repeat liver chemistries, liver event follow up assessments (see below), and close monitoring.
- A specialist or hepatology consultation is recommended.
- Monitor subjects twice weekly until liver chemistries (ALT, AST, alkaline phosphatase, bilirubin) resolve, stabilize or return to within baseline values.

For criteria 2, 3, 4 and 5:

- Make every reasonable attempt to have subjects return to clinic **within 24-72 hrs** for repeat liver chemistries and liver event follow up assessments (see below).

- Monitor subjects weekly until liver chemistries (ALT, AST, alkaline phosphatase, bilirubin) resolve, stabilize or return to within baseline values; criterion 5 subjects should be monitored as frequently as possible.

Subjects with ALT $\geq 5xULN$ and $< 8xULN$ which exhibit a decrease to ALT $x \geq 3xULN$, but $< 5xULN$ and bilirubin $< 2xULN$ without hepatitis symptoms or rash, and who can be monitored weekly for 4 weeks:

- Notify the Quintiles and Amicus medical monitor within 24 hours of learning of the abnormality to discuss subject safety.
- Can continue investigational product.
- Must return weekly for repeat liver chemistries (ALT, AST, alkaline phosphatase, bilirubin) until they resolve, stabilize or return to within baseline.
- If at any time these subjects meet the liver chemistry stopping criteria, proceed as described above.
- If, after 4 weeks of monitoring, ALT $< 3xULN$ and bilirubin $< 2xULN$, monitor subjects twice monthly until liver chemistries normalize or return to within baseline values.

For criteria 1-5, make every attempt to carry out the **liver event follow up assessments** described below:

- Viral hepatitis serology including:
 - Hepatitis A IgM antibody;
 - Hepatitis B surface antigen and Hepatitis B Core Antibody (IgM);
 - Hepatitis C ribonucleic acid (RNA);
 - Cytomegalovirus IgM antibody;
 - Epstein-Barr viral capsid antigen IgM antibody (or if unavailable, obtain heterophile antibody or monospot testing);
 - Hepatitis E IgM antibody
- Blood sample for pharmacokinetic (PK) analysis, obtained within 72 hours of last dose. Record the date/time of the PK blood sample draw and the date/time of the last dose of investigational product prior to blood sample draw on the CRF. If the date or time of the last dose is unclear, provide the subject's best approximation. If the date/time of the last dose cannot be approximated or a PK sample cannot be collected in the time period indicated above, do not obtain a PK sample. Instructions for sample handling and shipping are in the SPM/ISFN.
- Serum creatine phosphokinase (CPK) and lactate dehydrogenase (LDH).
- Fractionate bilirubin, if total bilirubin $\geq 2xULN$.
- Obtain complete blood count with differential to assess eosinophilia.

- Record the appearance or worsening of clinical symptoms of hepatitis or hypersensitivity, such as fatigue, nausea, vomiting, right upper quadrant pain or tenderness, fever rash, or eosinophilia as relevant on the AE report form.
- Record use of concomitant medications, acetaminophen, herbal remedies, other over the counter medications, or putative hepatotoxins, on the concomitant medications report form.
- Record alcohol use on the liver event alcohol intake case report form.

The following are required for subjects with ALT ≥ 3 xULN and bilirubin ≥ 2 xULN (>35% direct) but are optional for other abnormal liver chemistries:

- Anti-nuclear antibody, anti-smooth muscle antibody, and Type 1 anti-liver kidney microsomal antibodies.
- Serum acetaminophen adduct assay (quantifies potential acetaminophen contribution to liver injury, detectable by HPLC assay more than 1 week following acetaminophen use)(James, Letzig et al. 2009).
- Only in those with underlying chronic hepatitis B at study entry (identified by positive hepatitis B surface antigen): quantitative hepatitis B DNA and hepatitis delta antibody.
- Liver imaging (ultrasound, magnetic resonance, or computerized tomography) to evaluate liver disease.

